4.3. DESCRIPTION OF TREATMENTS

The following IMPs will be used in the study:

- Arm A: Combo Target (LGX818 450 mg p.o. od + MEK162 45 mg p.o. bid) until PD; then Combo Immuno (nivolumab 1 mg/kg solution i.v.combined with ipilimumab 3 mg/kg solution i.v.every 3 weeks for 4 doses then nivolumab 3 mg/kg solution i.v.every 2 weeks) until PD.
- Arm B: Combo Immuno (nivolumab 1 mg/kg solution i.v.combined with ipilimumab 3 mg/kg solution i.v.every 3 weeks for 4 doses then nivolumab 3 mg/kg solution i.v.every 2 weeks) until PD; then Combo Target (LGX818 450 mg p.o. od + MEK162 45 mg p.o. bid) until PD.
- Arm C: Combo Target (LGX818 450 mg p.o. od + MEK162 45 mg p.o. bid) for 8 weeks followed by Combo Immuno (nivolumab 1 mg/kg solution i.v.combined with ipilimumab 3 mg/kg solution i.v.every 3 weeks for 4 doses then nivolumab 3 mg/kg solution i.v.every 2 weeks) until PD; then Combo Target (LGX818 450 mg p.o. od + MEK162 45 mg p.o. bid) until PD.

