7. DEFINITION OF ANALYSIS SETS AND SUBGROUPS

Agreement and authorization of patients included/excluded from each analysis set will be performed on a case-by-case basis before the database lock.

The following analysis sets have been defined for this study:

Enrolled Analysis Set [ENR]

The all patients enrolled (ENR) set contains all patients who provided informed consent for this study.

Intent-to-Treat set [ITT]

The Intent-to-Treat (ITT) set will contain all randomized patients. Subjects in the ITT population will be analysed in the treatment group to which they were assigned by the randomization schedule, regardless of which study drug they receive.

The analysis of primary and secondary variables will be carried out in the ITT set.

Safety Analysis Set [SAF]

The Safety Analysis set (SAF) will contain all randomized subjects who received at least one dose of study medication. Subjects in the SAF will be analysed in the treatment group for the study drug they actually received.

The analysis of safety will be carried out in the safety population. If there is any doubt whether a subject was treated or not, they will be assumed treated for the purposes of analysis.

Per Protocol Analysis Set [PP]

The Per Protocol Analysis set (PP) will contain all randomized subjects who did not report any major protocol deviations (as detailed [Paragraph 6](#)).

The analysis on the primary variable (OS) will be repeated in the PP.

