21.1. ADVERSE EVENTS

All adverse events (AEs) reported on eCRF and experienced by the patient on or after the informed consent date will be considered in the analysis. Thus, there will not be derivation to Treatment-emerged Adverse Events (TEAE) and not TEAE.

Adverse event Investigator terms will be assigned to a Preferred Term (PT) and will be classified by primary System Organ Class (SOC) according to the Medical Dictionary for Regulatory Activities (MedDRA) thesaurus, version 20.0 or higher

Counts and percentages will be presented by primary System Organ Class (SOC) and Preferred Term (PT) as defined in MedDRA thesaurus, by treatment arm.

A patient having more than one AE with the same PT will be counted only once in the incidence calculation for that PT. Similarly, if a patient has more than one AE in the same SOC, the patient will be counted only once in the total number of patients with an AE for that SOC.

An AE will be defined “Related” if causality is “Certain”, “Probable” or “Possible”.

The following frequency distributions of adverse events will be provided by treatment arm:

- An overview of AEs including the number of patients with:
 - at least one AE,
 - at least one non-serious AE,
 - at least one AE related to Ipilimumab,
 - at least one AE related to Nivolumab,
 - at least one AE related to Combo Immuno Therapy,
 - at least one AE related to LGX818,
 - at least one AE related to MEK162,
 - at least one AE related to Combo Target Therapy,
 - at least one serious AE (SAE),
 - at least one SAE related to Ipilimumab,
 - at least one SAE related to Nivolumab,
 - at least one SAE related to Combo Immuno Therapy,
 - at least one SAE related to LGX818,
 - at least one SAE related to MEK162,
 - at least one SAE related to Combo Target Therapy,
 - at least one AE leading to hospitalization,
 - at least one AE leading to withdrawal from the study,

- at least on AESI,
and the number of AEs, non-serious AEs, SAEs, AEs related to Ipilimumab, AEs related to Nivolumab, AEs related to Combo Immuno Therapy, AEs related to LGX818, AEs related to MEK162, AEs related to Combo Target Therapy, SAEs related to Ipilimumab, SAEs related to Nivolumab, SAEs related to Combo Immuno Therapy, SAEs related to LGX818, SAEs related to MEK162, SAEs related to Combo Target Therapy, AEs leading to hospitalization, AEs leading to death, AEs leading to study withdrawal, AESIs;
- AEs presented by Primary SOC and PT;

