Number of SAEs related to Combo LGX818	n	xx	xx	xx
Number of SAEs related to Combo MEK162	n	xx	xx	xx
Number of SAEs related to Combo Target Therapy	n	xx	xx	xx
Number of AEs leading to hospitalization	n	xx	xx	xx
Number of AEs leading to death	n	xx	xx	xx
Number of AEs leading to withdrawal from the study	n	xx	xx	xx
Number of AEs of special interest (AESI)	n	xx	xx	xx
Number of Patients with at Least One AE	n (%)	xx (xx.x%)	xx (xx.x%)	xx (xx.x%)
Number of Patients with at Least One non-serious AE	n (%)	xx (xx.x%)	xx (xx.x%)	xx (xx.x%)
Number of Patients with at Least One AE related to Ipilimumab	n (%)	xx (xx.x%)	xx (xx.x%)	xx (xx.x%)
Number of Patients with at Least One AE related to Nivolumab	n (%)	xx (xx.x%)	xx (xx.x%)	xx (xx.x%)
Number of Patients with at Least One AE related to Combo Immuno Therapy	n (%)	xx (xx.x%)	xx (xx.x%)	xx (xx.x%)
Number of Patients with at Least One AE related to LGX818	n (%)	xx (xx.x%)	xx (xx.x%)	xx (xx.x%)
Number of Patients with at Least One AE related to MEK162	n (%)	xx (xx.x%)	xx (xx.x%)	xx (xx.x%)
Number of Patients with at Least One AE related to Combo Target Therapy	n (%)	xx (xx.x%)	xx (xx.x%)	xx (xx.x%)
Number of Patients with at Least One serious AE (SAE)	n (%)	xx (xx.x%)	xx (xx.x%)	xx (xx.x%)
Number of Patients with at Least One SAE related to Ipilimumab	n (%)	xx (xx.x%)	xx (xx.x%)	xx (xx.x%)
Number of Patients with at Least One SAE related to Nivolumab	n (%)	xx (xx.x%)	xx (xx.x%)	xx (xx.x%)
Number of Patients with at Least One SAE related to Combo Immuno Therapy	n (%)	xx (xx.x%)	xx (xx.x%)	xx (xx.x%)
Number of Patients with at Least One SAE related to Combo LGX818	n (%)	xx (xx.x%)	xx (xx.x%)	xx (xx.x%)
Number of Patients with at Least One SAE related to Combo MEK162	n (%)	xx (xx.x%)	xx (xx.x%)	xx (xx.x%)
Number of Patients with at Least One SAE related to Combo Target Therapy	n (%)	xx (xx.x%)	xx (xx.x%)	xx (xx.x%)
Number of Patients with at Least One AE leading to hospitalization	n (%)	xx (xx.x%)	xx (xx.x%)	xx (xx.x%)
Number of Patients with at Least One AE leading to withdrawal from the study	n (%)	xx (xx.x%)	xx (xx.x%)	xx (xx.x%)
Number of Patients with at Least One AESI	n (%)	xx (xx.x%)	xx (xx.x%)	xx (xx.x%)

Note: a) Percentages are calculated relative to the total number of patients in the SAF population by treatment arm.

b) An AE is defined as "related" to a study drug if relationship is "Certain", "Probable" or "Possible" to that specific drug. Missing data were considered as Related.

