<PT>	n (%) E	xx (xx.x%) xx	xx (xx.x%) xx	xx (xx.x%) xx

Note: a) Percentages are calculated relative to the total number of patients in the SAF Population by treatment arm.
 b) Each patient is counted at most once within each SOC and PT.
 c) AEs were coded using MedDRA version XX.X.
 d) n = number of patients, E = number of events.
 e) An AE is "related" to a study drug if relationship is "Certain", "Probable" or "Possible". Missing data were considered as Related.

Source: XXXX.SAS, Run on DDMMYYYY

TABLE 48. Incidence of Nivolumab-related AEs by primary System Organ Class and Preferred Term

POPULATION: SAF

	Statistic	Arm A (N = XX)	Arm B (N = XX)	Arm C (N = XX)
<Primary SOC>	n (%) E	xx (xx.x%) xx	xx (xx.x%) xx	xx (xx.x%) xx
<PT>	n (%) E	xx (xx.x%) xx	xx (xx.x%) xx	xx (xx.x%) xx
<PT>	n (%) E	xx (xx.x%) xx	xx (xx.x%) xx	xx (xx.x%) xx
<PT>	n (%) E	xx (xx.x%) xx	xx (xx.x%) xx	xx (xx.x%) xx
<Primary SOC>	n (%) E	xx (xx.x%) xx	xx (xx.x%) xx	xx (xx.x%) xx
<PT>	n (%) E	xx (xx.x%) xx	xx (xx.x%) xx	xx (xx.x%) xx
<PT>	n (%) E	xx (xx.x%) xx	xx (xx.x%) xx	xx (xx.x%) xx
<PT>	n (%) E	xx (xx.x%) xx	xx (xx.x%) xx	xx (xx.x%) xx
<Primary SOC>	n (%) E	xx (xx.x%) xx	xx (xx.x%) xx	xx (xx.x%) xx
<PT>	n (%) E	xx (xx.x%) xx	xx (xx.x%) xx	xx (xx.x%) xx
<PT>	n (%) E	xx (xx.x%) xx	xx (xx.x%) xx	xx (xx.x%) xx
<PT>	n (%) E	xx (xx.x%) xx	xx (xx.x%) xx	xx (xx.x%) xx
<Primary SOC>	n (%) E	xx (xx.x%) xx	xx (xx.x%) xx	xx (xx.x%) xx
<PT>	n (%) E	xx (xx.x%) xx	xx (xx.x%) xx	xx (xx.x%) xx
<PT>	n (%) E	xx (xx.x%) xx	xx (xx.x%) xx	xx (xx.x%) xx
<PT>	n (%) E	xx (xx.x%) xx	xx (xx.x%) xx	xx (xx.x%) xx

Note: a) Percentages are calculated relative to the total number of patients in the SAF Population by treatment arm.
 b) Each patient is counted at most once within each SOC and PT.
 c) AEs were coded using MedDRA version XX.X.
 d) n = number of patients, E = number of events.
 e) An AE is "related" to a study drug if relationship is "Certain", "Probable" or "Possible". Missing data were considered as Related.

Source: XXXX.SAS, Run on DDMMYYYY

TABLE 49. Incidence of Combo Immuno Therapy-related AEs by primary System Organ Class and Preferred Term

POPULATION: SAF

	Statistic	Arm A (N = XX)	Arm B (N = XX)	Arm C (N = XX)
<Primary SOC>	n (%) E	xx (xx.x%) xx	xx (xx.x%) xx	xx (xx.x%) xx
<PT>	n (%) E	xx (xx.x%) xx	xx (xx.x%) xx	xx (xx.x%) xx
<PT>	n (%) E	xx (xx.x%) xx	xx (xx.x%) xx	xx (xx.x%) xx
<PT>	n (%) E	xx (xx.x%) xx	xx (xx.x%) xx	xx (xx.x%) xx

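### Drug-related AE percentages are given only over all treated patients in the arm; for drugs that start after progression, an exposed-patient N and percentage should be added beside them

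*Supplement*

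**What the plan says.** Section 21.1 of the SAP states that "The following frequency distributions of adverse events will be provided by treatment arm" and lists, among these, tables of AEs related to ipilimumab, nivolumab, Combo Immuno, LGX818, MEK162 and Combo Target. These are shells 47 to 52 in section 26 (the list of tables that opens that section numbers them two lower). Each carries the note "Percentages are calculated relative to the total number of patients in the SAF Population by treatment arm". Shell 45, the AE overview, has patient rows for drug-related AEs and SAEs with an equivalent note: "Percentages are calculated relative to the total number of patients in the SAF population by treatment arm".

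Section 7 defines the denominator: "The Safety Analysis set (SAF) will contain all randomized subjects who received at least one dose of study medication". Any study drug qualifies, not only the one in the table's title.

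Section 4.3 sets the order of the drugs. For Arm A it reads "Arm A: Combo Target (LGX818 450 mg p.o. od + MEK162 45 mg p.o. bid) until PD; then Combo Immuno". Arm B runs the other way, with Combo Immuno "until PD; then Combo Target (LGX818 450 mg p.o. od + MEK162 45 mg p.o. bid) until PD". Arm C gives Combo Target for 8 weeks, then Combo Immuno, then Combo Target again after progression.

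The plan expects some patients not to reach the later therapy. Section 20.2.1 has an event rule in total PFS for patients unable to complete the sequence. Section 11 lists, as a reason for withdrawal, no longer meeting the study criteria after the first progression.

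**The concern.** A table titled by drug will be read as the frequency of that drug's reactions among people who took it. For a drug in second position the printed percentage is something else: the frequency among everyone who started the sequence, including patients still on the first therapy and those who died or could not switch. The same drug then has a near-complete exposed share in one column and a lower one in the next, and the difference comes from its place in the sequence.

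Toxicity of the study drugs is a stated objective (sections 3.2 and 3.3). The columns will be read side by side even though section 8.3 rules out comparative tests. At stake is the reading of the drug-specific safety tables. The primary analysis and the sample size are untouched.

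**Working it through.** **No figure to reproduce.** The SAP states no AE rate and no share of patients expected to reach each drug. The check is of the denominator rule.

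**Relation.** If drug-related events arise only in exposed patients:

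reported % = (% among exposed) × (exposed patients / SAF patients in the arm).

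**Where the share falls below 1**, from section 4.3:
- Combo Target in Arms A and C, and Combo Immuno in Arm B, come first: share near 1, no dilution.
- Combo Immuno in Arm C follows an 8-week lead-in: dilution probably small.
- Combo Immuno in Arm A and Combo Target in Arm B follow progression: share below 1 for everyone who has not progressed, died first or did not switch.

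**Illustration.** Assume 50% of exposed patients have a given related AE, and 50% to 80% are exposed:
- 0.50 × 0.5 = 25%
- 0.50 × 0.6 = 30%
- 0.50 × 0.7 = 35%
- 0.50 × 0.8 = 40%

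In whole patients, with an SAF arm of 69 (the planned minimum randomised per arm in section 4.2):
- 55 exposed, 28 with the event: 28/69 = 40.6% printed, 28/55 = 50.9% among exposed.
- 34 exposed, 17 with the event: 17/69 = 24.6% printed, 17/34 = 50.0% among exposed.

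**Is the assumed share plausible?** Section 4.2 assumes median PFS of about 10 months for Combo Target and 9.5 months for Combo Immuno. With an exponential model and a common follow-up time t, the share with a first PFS event is 1 − 0.5^(t/median):
- 24 months: 1 − 0.5^(24/10) = 81%; 1 − 0.5^(24/9.5) = 83%.
- 36 months: 1 − 0.5^(36/10) = 92%; 1 − 0.5^(36/9.5) = 93%.

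These counts include deaths, and not every patient who progresses switches, so at a given follow-up the exposed share would be lower. A 50% rate among exposed patients would show as at most about 41% at 24 months (0.50 × 0.83) or 46% at 36 months (0.50 × 0.93).

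**The numerator.** The notes to shells 45 and 47 to 52 count missing causality as related. As written, an Arm A patient who never had ipilimumab but has an AE with blank causality for it can enter the ipilimumab numerator, which works against the dilution. In the first whole-patient example, 14 of 69 are unexposed. If 7 of those 14 entered this way, the printed figure would be (28 + 7)/69 = 50.7%, close to the 50.9% among exposed. The understatement is therefore likely but not guaranteed, and any offset would be an accident of missing data.

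**Other outputs.** The counts of patients and events in shells 47 to 52 are not diluted. Shell 23 has an n for exposure to each drug by arm, but it is headed ITT (section 19 says SAF) and no AE percentage uses it. Section 21.1 plans no exposed-only percentage. Restricted denominators are not foreign to this SAP: mutation type is divided by patients with a mutation, and ECG interpretation by those with an abnormal ECG.

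**The case against.** The strongest reply is that the denominator fits the objective as written. Sections 3.2 and 3.3 ask about the effects and safety of the sequencing treatments. A patient in Arm A who never reaches ipilimumab is spared its toxicity, and the per-arm incidence records that correctly. This stands, and it is why the all-SAF percentage should stay. A reader might infer that the denominator is simply wrong, or that a lower figure for a second-position drug is a spurious advantage. The documents do not support that reading: for the sequence question the lower figure is real.

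An exposed-only percentage has a fault of its own. It conditions on progression, survival and switching, all after randomisation, so first-line and second-line recipients are differently selected. This also stands: the added figure describes recipients and is not a randomised comparison.

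Much can be recovered by hand from the undiluted counts, shell 23 and the dosing listings (42 to 47). That lowers the priority, but a reader of the tables alone cannot do it.

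Two further remedies are tempting and not supported at present. An event rate per patient-month would rest on the section 19.1 exposure, which sums end date minus start date plus one over cycles. The nivolumab and ipilimumab listings (45 and 46) show a start date and infusion times but no end date, and nothing says whether the end date in Listing 42 is the infusion day or the end of the cycle. If it is the infusion day, four ipilimumab doses amount to about four days. Splitting Arm C's two Combo Target blocks would need a rule assigning AEs to periods, which the SAP lacks.

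**Conclusion.** The concern holds as a gap in presentation. Tables titled by drug give only a per-sequence incidence. For Combo Immuno in Arm A and Combo Target in Arm B, that incidence is diluted, relative to the rate among recipients, by the share of the arm who reached the drug. No planned output supplies the rate among recipients.

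The size is unknown. The 25% to 40% illustration rests on an assumed 50% event rate, an assumed exposed share of 50% to 80%, and related events arising only in exposed patients. The missing-causality rule can breach the last of these, so the direction is probable, not certain. The point is a cheap improvement to the safety tables; no decision rule depends on it.

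**What to change.** In shells 47 to 52 and the drug-related AE and SAE patient rows of shell 45:

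1. Keep the all-SAF percentage and label it as incidence per assigned sequence.
2. Beside it, for each drug or combination and each arm, print the number of SAF patients who received at least one dose of it and the percentage among those patients. For combinations, state whether one component is enough to count as exposed.
3. Restrict the numerator of the added percentage to exposed patients, so that the missing-causality rule cannot bring in patients who never had the drug.
4. Add a footnote that the added percentage conditions on progression, survival and switching, and is descriptive.

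Do not add a patient-month rate unless the section 19.1 dates are shown to span the dosing interval for the infusions.

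The cost is a paragraph in section 21.1, revised footnotes and extra columns, using dosing data already collected. The downside is two denominators per table and exposed groups that are selected, which the footnote has to make plain.

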9.3. MISSING DATA

Any Missing data will not be imputed (including efficacy data).

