Week <Every 12 wks> - Combo Target	n	xx	xx
	Mean (SD)	xx.x (x.x)	xx.x (x.x)
	Median	xx.x	xx.x
	Min/Max	xx/xx	xx/xx

Notes:

(*) Change from baseline is calculated relative to Baseline 1 for values between Baseline 1 and Baseline 2; Baseline 2 for values after Baseline 2. Change from baseline values include only those patients with both a Baseline value and a value for summarized time period. n represents number of patients contributing to summary statistics.

Source: XXXX.SAS, Run on DDMMYYYY

TABLE 87. ECG Parameters - ARM C

POPULATION: SAF < Note for SAS Programmer: the following must be presented for continuous values of URBC/HPF, Bacteria, Other as well >

	Statistic	Value	Change from Baseline (*)
PR interval (ms)			
Baseline 1	n	xx	
	Mean (SD)	xx.x (x.x)	
	Median	xx.x	
	Min/Max	xx/xx	
Week 4 - Combo Target	n	xx	xx
	Mean (SD)	xx.x (x.x)	xx.x (x.x)
	Median	xx.x	xx.x
	Min/Max	xx/xx	xx/xx
Baseline 2	n	xx	
	Mean (SD)	xx.x (x.x)	
	Median	xx.x	
	Min/Max	xx/xx	
Week 4 - Nivolumab + Ipilimumab	n	xx	xx
	Mean (SD)	xx.x (x.x)	xx.x (x.x)
	Median	xx.x	xx.x
	Min/Max	xx/xx	xx/xx
Week <Every 12 wks> - Nivolumab	n	xx	xx
	Mean (SD)	xx.x (x.x)	xx.x (x.x)
	Median	xx.x	xx.x
	Min/Max	xx/xx	xx/xx
Baseline 3	n	xx	
	Mean (SD)	xx.x (x.x)	
	Median	xx.x	
	Min/Max	xx/xx	
Week 4 - Combo Target	n	xx	xx
	Mean (SD)	xx.x (x.x)	xx.x (x.x)
	Median	xx.x	xx.x
	Min/Max	xx/xx	xx/xx
Week <Every 12 wks> - Combo Target	n	xx	xx
	Mean (SD)	xx.x (x.x)	xx.x (x.x)
	Median	xx.x	xx.x
	Min/Max	xx/xx	xx/xx

Notes:

(*) Change from baseline is calculated relative to Baseline 1 for values between Baseline 1 and Baseline 2; Baseline 2 for values between Baseline 2 and Baseline 3; Baseline 3 for values after Baseline 3. Change from baseline values include only those patients with both a Baseline value and a value for summarized time period.
n represents number of patients contributing to summary statistics.

Source: XXXX.SAS, Run on DDMMYYYY

TABLE 88. Cardiological Assessments - ARM A

POPULATION: SAF

< Note for SAS Programmer: the following must be presented for each visit during the study >

	Statistic	Arm A (N=XX)
<Visit n>		
ECG Result		
Normal	n (%)	xx (xx.x%)
Abnormal	n (%)	xx (xx.x%)
Interpretation of abnormality (*)		
Not clinically significant	n (%)	xx (xx.x%)
Clinically significant	n (%)	xx (xx.x%)
Type of LVEF scan		
ECHO	n (%)	xx (xx.x%)
MUGA	n (%)	xx (xx.x%)
Interpretation of ECHO/MUGA scan		
Normal	n (%)	xx (xx.x%)
Abnormal, NCS	n (%)	xx (xx.x%)
Normal, CS	n (%)	xx (xx.x%)

Notes:

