Percentages are calculated relative to the total number of patients of ARM A in the SAF set.

(*) Percentages are calculated relative to the total number of patients of ARM A in the SAF set with abnormal ECG.

NCS = Not Clinically Significant; CS = Clinically Significant.

Source: XXXX.SAS, Run on DDMMYYYY

TABLE 89. Cardiological Assessments - ARM B

POPULATION: SAF

< Note for SAS Programmer: the following must be presented for each visit during the study >

	Statistic	Arm B (N=XX)
<Visit n>		
ECG Result		
Normal	n (%)	xx (xx.x%)
Abnormal	n (%)	xx (xx.x%)
Interpretation of abnormality (*)		
Not clinically significant	n (%)	xx (xx.x%)
Clinically significant	n (%)	xx (xx.x%)
Type of LVEF scan		
ECHO	n (%)	xx (xx.x%)
MUGA	n (%)	xx (xx.x%)
Interpretation of ECHO/MUGA scan		
Normal	n (%)	xx (xx.x%)
Abnormal, NCS	n (%)	xx (xx.x%)
Normal, CS	n (%)	xx (xx.x%)

Notes:

Percentages are calculated relative to the total number of patients of ARM B in the SAF set.

(*) Percentages are calculated relative to the total number of patients of ARM B in the SAF set with abnormal ECG.

NCS = Not Clinically Significant; CS = Clinically Significant.

Source: XXXX.SAS, Run on DDMMYYYY

TABLE 90. Cardiological Assessments - ARM C

POPULATION: SAF < Note for SAS Programmer: the following must be presented for each visit during the study >

	Statistic	Arm C (N=XX)
<Visit n>		
ECG Result		
Normal	n (%)	xx (xx.x%)
Abnormal	n (%)	xx (xx.x%)
Interpretation of abnormality (*)		
Not clinically significant	n (%)	xx (xx.x%)
Clinically significant	n (%)	xx (xx.x%)
Type of LVEF scan		
ECHO	n (%)	xx (xx.x%)
MUGA	n (%)	xx (xx.x%)
Interpretation of ECHO/MUGA scan		
Normal	n (%)	xx (xx.x%)
Abnormal, NCS	n (%)	xx (xx.x%)
Normal, CS	n (%)	xx (xx.x%)

Notes:

Percentages are calculated relative to the total number of patients of ARM C in the SAF set.

(*) Percentages are calculated relative to the total number of patients of ARM C in the SAF set with abnormal ECG.

NCS = Not Clinically Significant; CS = Clinically Significant.

Source: XXXX.SAS, Run on DDMMYYYY

TABLE 91. Vital signs - ARM A

POPULATION: SAF < Note for SAS Programmer: the following must be presented for each vital sign >

	Statistic	Value	Change from Baseline (*)
Body weight (Kg)			
Baseline 1	n	xx	
	Mean (SD)	xx.x (x.x)	
	Median	xx.x	
	Min/Max	xx/xx	
Week <Every 4 wks> - Combo Target	n	xx	xx
	Mean (SD)	xx.x (x.x)	xx.x (x.x)
	Median	xx.x	xx.x
	Min/Max	xx/xx	xx/xx
Baseline 2	n	xx	
	Mean (SD)	xx.x (x.x)	
	Median	xx.x	

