Dermatological Examination performed		
No	n (%)	xx (xx.x%)
Yes	n (%)	xx (xx.x%)
Result (*)		
Normal	n (%)	xx (xx.x%)
Abnormal	n (%)	xx (xx.x%)
Diagnosis (§)		
Squamous cell carcinoma	n (%)	xx (xx.x%)
Keratoacanthomas	n (%)	xx (xx.x%)
Other pathology findings	n (%)	xx (xx.x%)
Evidence of severe or uncontrolled systemic disease or concurrent undesirable condition		
No	n (%)	xx (xx.x%)
Yes	n (%)	xx (xx.x%)

Notes:

Percentages are calculated relative to the total number of patients of ARM A in the SAF set.

(*) Percentages are calculated relative to the total number of patients of ARM A in the SAF set who performed the dermatological examination.

(§) Percentages are calculated relative to the total number of patients of ARM A in the SAF set who resulted abnormal.

Source: XXXX.SAS, Run on DDMMYYYY

TABLE 101. Dermatological examination during the study - ARM B

POPULATION: SAF < Note for SAS Programmer: the following must be presented for each visit: Baseline 1, Q8W, Baseline 2, Q8W >

	Statistic	Arm B (N=XX)
<Visit n>		
Dermatological Examination performed		
No	n (%)	xx (xx.x%)
Yes	n (%)	xx (xx.x%)
Result (*)		
Normal	n (%)	xx (xx.x%)
Abnormal	n (%)	xx (xx.x%)
Diagnosis (§)		
Squamous cell carcinoma	n (%)	xx (xx.x%)
Keratoacanthomas	n (%)	xx (xx.x%)
Other pathology findings	n (%)	xx (xx.x%)
Evidence of severe or uncontrolled systemic disease or concurrent undesirable condition		
No	n (%)	xx (xx.x%)
Yes	n (%)	xx (xx.x%)

Notes:

Percentages are calculated relative to the total number of patients of ARM B in the SAF set.

(*) Percentages are calculated relative to the total number of patients of ARM B in the SAF set who performed the dermatological examination.

(§) Percentages are calculated relative to the total number of patients of ARM B in the SAF set who resulted abnormal.

Source: XXXX.SAS, Run on DDMMYYYY

TABLE 102. Dermatological examination during the study - ARM C

POPULATION: SAF < Note for SAS Programmer: the following must be presented for each visit: Baseline 1, Baseline 2, Q8W, Baseline 3>

	Statistic	Arm C (N=XX)
<Visit n>		
Dermatological Examination performed		
No	n (%)	xx (xx.x%)
Yes	n (%)	xx (xx.x%)
Result (*)		
Normal	n (%)	xx (xx.x%)
Abnormal	n (%)	xx (xx.x%)
Diagnosis (§)		
Squamous cell carcinoma	n (%)	xx (xx.x%)
Keratoacanthomas	n (%)	xx (xx.x%)
Other pathology findings	n (%)	xx (xx.x%)
Evidence of severe or uncontrolled systemic disease or concurrent undesirable condition		
No	n (%)	xx (xx.x%)
Yes	n (%)	xx (xx.x%)

Notes:

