Percentages are calculated relative to the total number of patients of ARM C in the SAF set.

(*) Percentages are calculated relative to the total number of patients of ARM C in the SAF set who performed the dermatological examination.

(§) Percentages are calculated relative to the total number of patients of ARM C in the SAF set who resulted abnormal.

Source: XXXX.SAS, Run on DDMMYYYY

TABLE 103. Performance Status during the study - ARM A

POPULATION: SAF

ECOG PS	Statistic	Arm A (N=XX)
<Visit n>		
0	n (%)	xx (xx.x%)
1	n (%)	xx (xx.x%)
2	n (%)	xx (xx.x%)
3	n (%)	xx (xx.x%)
4	n (%)	xx (xx.x%)
5	n (%)	xx (xx.x%)

Notes:

Percentages are calculated relative to the total number of patients of the SAF set in the ARM A.

Source: XXXX.SAS, Run on DDMMYYYY

< Note for SAS Programmer: In this table ECOG PS at all visits must be reported.>

TABLE 104. Performance Status during the study - ARM B

POPULATION: SAF

ECOG PS	Statistic	Arm B (N=XX)
<Visit n>		
0	n (%)	xx (xx.x%)
1	n (%)	xx (xx.x%)
2	n (%)	xx (xx.x%)
3	n (%)	xx (xx.x%)
4	n (%)	xx (xx.x%)
5	n (%)	xx (xx.x%)

Notes:

Percentages are calculated relative to the total number of patients of the SAF set in the ARM B.

Source: XXXX.SAS, Run on DDMMYYYY

< Note for SAS Programmer: In this table ECOG PS at all visits must be reported.>

TABLE 105. Performance Status during the study - ARM C

POPULATION: SAF

ECOG PS	Statistic	Arm C (N=XX)
<Visit n>		
0	n (%)	xx (xx.x%)
1	n (%)	xx (xx.x%)
2	n (%)	xx (xx.x%)
3	n (%)	xx (xx.x%)
4	n (%)	xx (xx.x%)
5	n (%)	xx (xx.x%)

Notes:

Percentages are calculated relative to the total number of patients of the SAF set in the ARM C.

Source: XXXX.SAS, Run on DDMMYYYY

< Note for SAS Programmer: In this table ECOG PS at all visits must be reported.>

TABLE 106. Pregnancy test during the study

POPULATION: SAF

ECOG PS	Statistic	Arm A (N=XX)	Arm B (N=XX)	Arm C (N=XX)
Baseline 1				
Negative	n (%)	xx (xx.x%)	xx (xx.x%)	xx (xx.x%)
Positive	n (%)	xx (xx.x%)	xx (xx.x%)	xx (xx.x%)
<Every 6 weeks>				
Negative	n (%)	xx (xx.x%)	xx (xx.x%)	xx (xx.x%)
Positive	n (%)	xx (xx.x%)	xx (xx.x%)	xx (xx.x%)
Follow-up visit				
Negative	n (%)	xx (xx.x%)	xx (xx.x%)	xx (xx.x%)
Positive	n (%)	xx (xx.x%)	xx (xx.x%)	xx (xx.x%)
Long-term follow-up visit				
Negative	n (%)	xx (xx.x%)	xx (xx.x%)	xx (xx.x%)
Positive	n (%)	xx (xx.x%)	xx (xx.x%)	xx (xx.x%)

Notes:

Percentages are calculated relative to the total number of female patients of the SAF set by treatment arm.

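### By-visit urinalysis, ECG/LVEF and ECOG percentages use the whole safety-set arm as denominator, so attrition scales them down and they are not comparable across visits, blocks or arms

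*Supplement*

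**What the plan says.** Table numbers here are those on the shells in SAP section 26; the list of tables that opens that section numbers the same tables two lower.

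- **Urinalysis (Tables 76-81) and ECG result/LVEF scan (Tables 88-90).** The Arm A note reads "Percentages are calculated relative to the total number of patients of ARM A in the SAF set". Arms B and C carry the same note with the arm changed.
- **ECOG performance status (Tables 103-105).** The Arm A note is equivalent: "Percentages are calculated relative to the total number of patients of the SAF set in the ARM A".
- **Repetition by visit.** The programmer note on Tables 88-90 says "the following must be presented for each visit during the study". The urinalysis shells list the visits of each treatment block, and the ECOG shells ask for all visits.
- **The set itself.** Section 7: "The Safety Analysis set (SAF) will contain all randomized subjects who received at least one dose of study medication". Membership does not change with visit.
- **Missing values.** Section 9.3 imputes nothing, and these shells have no row for assessments not done.
- **Different denominators elsewhere.** The ECG interpretation rows are conditional: "Percentages are calculated relative to the total number of patients of ARM A in the SAF set with abnormal ECG". The dermatology result rows use "Percentages are calculated relative to the total number of patients of ARM A in the SAF set who performed the dermatological examination". Ophthalmology sub-items also divide by patients examined, and the continuous-parameter tables print the contributing n at each visit.

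Sections 21.2, 21.3 and 23.3 set no by-visit denominator, and section 24.1 makes the shells binding for the output.

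**The concern.** At any visit after baseline some patients of the arm have no value, because they have progressed, died, stopped, or not reached the block in question. Under these notes they stay in the denominator without entering any category. The printed percentage then mixes two quantities: how common the finding is among patients examined, and how many patients are still being examined.

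The second factor differs by visit, by block and by arm. Under section 4.3, combo immuno starts at randomization in Arm B, after progression in Arm A, and after 8 weeks of combo target in Arm C. The same true rate of abnormal ECG on combo immuno would print at different levels in the three arms simply because different shares of each arm reach and remain in that block. Safety of the sequences is a stated objective (section 3.3), so a reader will set these tables side by side.

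**Working it through.** **Plan's own figures.** The SAP states no expected value for these percentages. The arm size used below is its 69 per arm (section 4.2). That figure reproduces: with 33% and 48% alive at 24 months, a rule of at least 30 of 69 has an exact one-sided alpha of 0.0446 and power of 0.808.

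**Identity.** For a category at visit *v*:

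printed % = (n in category / n assessed at *v*) × (n assessed at *v* / N of arm in SAF)

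The first factor is the rate of interest. The second is the share assessed, and it does not depend on the rate.

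**Illustration, first block.** Assumptions:
- all 69 patients are in the SAF and assessed at baseline;
- time on the first treatment is exponential, with the 10-month planning median PFS for combo target (section 4.2);
- the true abnormality rate is constant at 10% of those assessed (not a document figure);
- one month is 4.345 weeks.

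Share assessed at week *w* = 0.5^((*w*/4.345)/10).

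| Week | Share assessed | Assessed of 69 | 10% prints as |
|---|---|---|---|
| 4 | 0.938 | 65 | 9.4% |
| 24 | 0.682 | 47 | 6.8% |
| 48 | 0.465 | 32 | 4.6% |
| 96 | 0.216 | 15 | 2.2% |

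At week 48 the true rate would have to be 10% / 0.465 = 21.5% for the table to keep showing 10%. All categories together sum to 46.5% at that visit.

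**Illustration, combo immuno at week 24 of the block.** With the 9.5-month planning median, the share of starters still assessed is 0.5^((24/4.345)/9.5) = 0.668.
- Arm B, where it is the first block: 10% × 0.668 = 6.7%.
- Arm A, where it is the second block, assuming 60% to 80% of patients start it: 10% × 0.6 × 0.668 = 4.0%, to 10% × 0.8 × 0.668 = 5.3%.

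The treatment and the true rate are the same, but the printed rates differ.

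**Where the effect is small.** Arm C's first block lasts 8 weeks, and its urinalysis shells show only Day 1 and Week 4 before Baseline 2. The week 4 factor is 0.94.

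**With the denominator corrected,** 10% prints as 10% at every visit in each illustration.

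**The case against.** The strongest reply is that nothing is hidden. The denominator is stated under each table, n is printed beside every percentage, and N stands in the column header. The ECG, dipstick and ECOG categories are exhaustive, so adding the counts gives the number assessed. Continuous ECG and urinalysis values have their own n by visit, section 21.3 plans ejection fraction values by visit in every arm, and the listings show whether each assessment was done. Section 8.3 excludes comparative tests. All of this stands and limits the consequence, but the printed percentage still does not describe the patients examined.

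It can also be said that the dermatology shells are not a clean contrast: only the rows that follow a performed/not-performed question use the reduced denominator, and their other rows use the full arm. That is fair, so this is not a direct contradiction between notes. The difference matters because the urinalysis, ECG/LVEF and ECOG shells have no performed row from which the reader could see attendance.

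Three stronger readings are tempting and are not supported:

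- **That every abnormality rate falls over time by construction.** The ECG interpretation rows divide by patients with an abnormal ECG and are not diluted in this way. Elsewhere the percentage falls only if the rate among those assessed does not outpace attrition. Each block restarts at a new baseline, and patients can reappear in the End of Treatment and Follow-up rows of the urinalysis shells.
- **That the tables cannot be interpreted.** The counts permit recalculation, and the ratio of normal to abnormal within a visit is unchanged because both shrink equally.
- **That arms with faster attrition will be judged safer.** Normal percentages shrink too, the tables are single-arm, and no decision rule uses them. What holds is that the percentages are not comparable between arms.

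**Conclusion.** The point holds as a fault of descriptive presentation that should be corrected. Following the notes multiplies each affected percentage by the share of the arm assessed at that visit. That identity needs no assumption. Its size does: about 0.68 at week 24 and 0.47 at week 48 if time on first treatment is exponential with a 10-month median, and about 0.40 to 0.53 at week 24 of a combo immuno second block with a 9.5-month median that 60% to 80% of patients start. The switch share is assumed, and planning PFS is only a proxy for visit attendance. No estimate of efficacy, test or go/no-go rule is affected.

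**What to change.** 1. In the notes to Tables 76-81, 88-90 and 103-105, define the denominator as safety-set patients of the arm with a non-missing result for that parameter at that visit.
2. Print that number at each visit. A row for not done/missing is a useful option, because it keeps attendance visible.
3. Leave the ECG interpretation rows conditional on an abnormal ECG and add that abnormal means at that visit; the present note does not say whether it means then or ever. Dividing these rows by all patients assessed would turn a correctly conditional percentage into a different quantity.

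The cost is a note edit and about one programming line per table, with no new data. The drawback is that late-visit percentages will rest on few patients, selected by still attending, which matters most for ECOG. The printed n shows the small numbers but does not remove the selection, so trends over visits still need cautious reading.
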